4 OVERALL STUDY DESIGN

This is a Phase 2, multicenter, randomized, double-masked, vehicle-controlled, parallel-group design with block enrollment. Subjects will be randomized to one of the following treatment groups at Visit 2:

- [REDACTED] K-161; [REDACTED] (N=~60)
- [REDACTED] K-161; [REDACTED] (N=~60)
- [REDACTED] K-161; [REDACTED] (N=~60)
- Placebo Ophthalmic Solution (Vehicle); [REDACTED] (N=~60)

Approximately 240 subjects will be randomly assigned to one of the four treatment groups (1:1:1:1). [REDACTED]

[REDACTED] Subjects, Sponsor, Contract research organization (CRO), and site personnel will be masked to treatment assignment. To ensure masking, a dedicated unmasked staff member/technician will be delegated to dispense and observe instillation of randomized study drug and collect randomized study drug from a subject for drug accountability. This person cannot perform any other study-related procedures. Additionally, the informed consent form (ICF) will not indicate any relationship between dosing regimen and treatment. Subjects will be instructed not to discuss their assigned dosing regimen or perceived treatment effects with other study participants.

During the screening period, two 90-minute exposures to the CAE will be conducted to ascertain eligibility to enter the study. Subjects who qualify after the initial screening visit will enter the run-in phase, where they will self-administer vehicle [REDACTED] for approximately 14 days. Those who qualify at Visit 2 (Day 1) will be randomized to receive study drug in a double-masked fashion for 28 days. Randomization will be stratified on Visit 2 Post-CAE inferior fluorescein staining and

Post-CAE ocular discomfort on the Ora Calibra® scale. Subjects will self-administer drops either [redacted] or [redacted]

At Visit 4 (Day 15) and Visit 5 (Day 29), CAE exposure will occur, with pre-CAE, during CAE (symptoms only) and post-CAE assessments of ocular signs and symptoms. At Visit 3, no CAE exposure will occur but signs and symptoms will be assessed. Study drug will be discontinued at Visit 5. Subjects will exit from the study at this visit. The follow-up phone call will occur about 7 days after the final day of randomized study drug treatment.

The timing of subject visits and examinations will be consistent throughout the study.

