10.4.2 Unit of Analysis

Safety endpoints will be analyzed for both eyes. For efficacy endpoints, the unit of analysis will be the study eye, or the “worst eye,” as defined by the following:

Worst Eye: Eyes are eligible for analysis if they meet all of the inclusion criteria. At least one eye (the right eye or the left eye) must meet all of the criterial. In the case that both eyes are eligible for analysis, the worst eye will be selected as the eye with the worst post-CAE inferior corneal staining at Visit 2. If the post-CAE inferior

corneal staining at Visit 2 is the same in both eyes then the eye with the worst post-CAE ODS at Visit 2 will be worst eye. If the post-CAE inferior corneal staining and ocular discomfort are the same in both eyes then the right eye will be selected as the worst eye.

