8.3 Definition of Baseline

Baseline is defined as the last measurement prior to the first dose of study medication. If a measure is taken both pre-CAE® and post-CAE®, the baseline will be the time point matched value. For changes from pre-CAE® to post-CAE® after the first treatment, the change from pre-CAE® to post-CAE® will be considered the baseline value.

For [REDACTED] baseline will be measurements taken at Visit 1 (Day -14).

Change from baseline will be calculated as follow-up visit minus baseline visit.

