13.1 Primary Analysis

The primary efficacy endpoints of the study are:

- Mean change from baseline in post-CAE® inferior corneal fluorescein staining score on the Ora Calibra® scale at Visit 5 (Day 29), comparing [REDACTED] K-161 [REDACTED] to vehicle [REDACTED]
- Mean change from baseline in post-CAE® ocular discomfort scale on the Ora Calibra® scale at Visit 5 (Day 29), comparing [REDACTED] K-161 [REDACTED] to vehicle [REDACTED]

Change from baseline for both endpoints will be calculated as Visit – Baseline, where a positive difference indicates a worsening of dry eye signs or symptoms and a negative difference indicates an improvement of dry eye signs or symptoms. Treatment comparisons between [REDACTED] K-161 [REDACTED] and vehicle [REDACTED] will be calculated as [REDACTED] K-161 [REDACTED] - vehicle [REDACTED]. All primary endpoints will be described in subject listings.

13.1.1 INFERIOR CORNEAL FLUORESCEIN STAINING SCORE AT VISIT 5 (DAY 29) POST-CAE, [REDACTED] K-161 [REDACTED] VS VEHICLE [REDACTED]

Fluorescein staining will be conducted at all visits at pre-CAE® and post-CAE®. Grading will be conducted using the Ora Calibra® Scale from 0 to 4 with the use of half grade (0.5) increments, where grade 0 = None and 4 = Severe. The regions to be assessed will be the central, superior, inferior, temporal, nasal, corneal sum, conjunctival sum, and total eye score for study eye only.

Inferior corneal fluorescein staining will be summarized at Visit 5 (Day 29) Post-CAE® by treatment groups using continuous descriptive statistics. Primary analysis will use an analysis of covariance (ANCOVA) model adjusted for baseline value, site, and with treatment group as the explanatory variable. Changes from baseline for each treatment group in inferior corneal fluorescein staining will be compared between [REDACTED] K-161 [REDACTED] and vehicle [REDACTED]. In addition, treatment by baseline and treatment by study site interactions will be explored in separate models to evaluate how the treatment effect may differ for baseline value and study sites. Analyses will be performed by baseline stratification (≤ 3.0 and >3.0) and/or site to understand how the treatment effect differs for baseline value and study sites. Least squares (LS) means for each treatment group and the LS mean difference between treatment groups will be presented from the models together with standard errors (SE), two-sided p-values, and two-sided 95% CIs.

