For the primary analysis, the primary efficacy endpoint of inferior corneal fluorescein staining will have missing data imputed using a control-based pattern mixture model under the assumption of a missing not at random mechanism. The imputation will first impute non-monotone missing data using MCMC to obtain a dataset with a monotone missing pattern, then a control-based pattern mixture model will be run. The SAS® code for obtaining multiple pattern mixture model imputation data is:

```

PROC MI DATA = INDATA SEED = 6849548 OUT = MDATA NIMPUTE = 100
      MINIMUM = 0 MAXIMUM = 4 ROUND = 0.5;
      BY TREATMENT;
      MCMC IMPUTE=MONOTONE;
      VAR BASELINE IFS4 IFS5;
      RUN;
  
```

```

PROC MI DATA = MDATA SEED = 3541655 OUT = OUTDATA NIMPUTE = 1
  
```

```

        MINIMUM = . 0 0 0 MAXIMUM = . 4 4 4 ROUND = . 0.5 0.5 0.5;
        BY _Imputation_;
        CLASS TREATMENT;

        MONOTONE REG(IF54 = BASELINE/ DETAILS);
        MONOTONE REG(IF55 = BASELINE IF54/ DETAILS);
        MNAR MODEL(IF54 IF55 / MODELOBS=(TREATMENT='Vehicle'));
        VAR BASELINE IF54 IF55;
RUN;

```

where

- *INDATA* is the name of the input dataset
- *MDATA* is the name an intermediary dataset with a monotone missing pattern
- *OUTDATA* is the name of the output dataset
- *TREATMENT* is the name of the treatment group variable
- *BASELINE* is the baseline inferior corneal fluorescein staining
- *IF54-IF55* are the inferior corneal fluorescein staining at Visits 4 (Day 15) through Visit 5 (Day 29)

If multiple pattern mixture model imputation fails to generate imputations, baseline total sum fluorescein staining score will be added to the `VAR` statement and multiple imputation will be reattempted. If multiple imputation still fails to generate the required imputation, then `MINIMUM`, `MAXIMUM`, and `ROUND` statements will be removed.

After the imputed data sets are obtained, the following code will be used to execute the ANCOVA model on each imputed data set and the results combined from the analyses:

```

PROC MIXED DATA = OUTDATA;
    BY _IMPUTATION_;
    CLASS TREATMENT SITE;
    MODEL CHG = BASELINE TREATMENT SITE/ SOLUTION COVB;
    LSMEANS TREATMENT / CL PDIFF;
    ODS OUTPUT LSMEANS = OUTLS DIFFS = OUTDIFFS;
RUN;

PROC SORT DATA=OUTLS; BY TREATMENT _IMPUTATION_; RUN;
PROC MIANALYZE DATA=OUTLS;
    BY TREATMENT;
    MODELEFFECTS ESTIMATE;
    STDERR STDERR;
RUN;

DATA OUTDIFFS;
    SET OUTDIFFS;
    COMPARISON = TREATMENT||' - '||LEFT(_TREATMENT);

```

```

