Two sample t-tests will be conducted as sensitivity analyses using pattern mixture model imputation with the ITT population, observed data only with the ITT population, LOCF imputation with the ITT population, MCMC imputation with the ITT population, and observed data only with the PP population. Wilcoxon rank sum tests will be conducted as sensitivity analyses using observed data only with the ITT population, LOCF imputation with the ITT population, and observed data only with the PP population.

LS Means for inferior corneal fluorescein staining changes from baseline pre-CAE® and post-CAE® at Visit 5 (Day 29) will be displayed graphically in a bar chart with 95% CI bars by treatment group based on the ANCOVA analysis of the pattern mixture model imputation with the ITT population.

13.1.2 OCULAR DISCOMFORT SCALE AT VISIT 5 (DAY 29) Post-CAE, [REDACTED] K-161 [REDACTED] vs VEHICLE [REDACTED]

Ocular discomfort scores will be subjectively graded by the subjects using the Ora Calibra® Ocular Discomfort Scale at all visits at pre-CAE® and post-CAE® for each eye separately. The Ocular Discomfort Scale ranges from 0 to 4 where 0 = No Discomfort, 1 = Intermittent Awareness, 2 = Constant Awareness, 3 = Intermittent Discomfort, and 4 = Constant Discomfort. Analyses will only be produced for the study eye.

Ocular discomfort will be summarized at Visit 5 (Day 29) Post-CAE® by treatment groups using continuous descriptive statistics. Primary analysis will use an ANCOVA model adjusted for baseline ocular discomfort, site, and with treatment group as the explanatory variable. Changes from baseline for each treatment group in ocular discomfort will be compared between [REDACTED] K-161 [REDACTED] and vehicle [REDACTED]. In addition, treatment by baseline and treatment by study site interactions will be explored in separate models to evaluate how the treatment effect may differ for baseline value and study sites. In the case of a significant interaction at the 0.05 level, analyses will be performed by baseline stratification (≤ 3.0 and > 3.0) and/or site to understand how the treatment effect differs for baseline value and study sites. Least squares means for each treatment

group and the LS mean difference between treatment groups will be presented from the models together with SE, two-sided p-values, and two-sided 95% CIs.

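### The four hierarchical ANCOVAs use the Visit 2 value as their only pre-treatment score and leave out the matching Visit 1 value already collected, a modest missed gain in precision

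*SAP*

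**What the plan says.** - **Models.** SAP 13.1.1 sets the staining model: "Primary analysis will use an analysis of covariance (ANCOVA) model adjusted for baseline value, site, and with treatment group as the explanatory variable". SAP 13.1.2 does the same for ODS: "Primary analysis will use an ANCOVA model adjusted for baseline ocular discomfort, site, and with treatment group as the explanatory variable". SAP 13.2.1 (Schirmer's) and 13.2.2 (TFBUT) repeat the structure. The code in 13.1.1 is "MODEL CHG = BASELINE TREATMENT SITE/ SOLUTION COVB".
- **Imputation.** The variable list for staining is "VAR BASELINE IFS4 IFS5", that is, baseline, Visit 4 and Visit 5.
- **Baseline.** SAP 8.3: "Baseline is defined as the last measurement prior to the first dose of study medication", and "If a measure is taken both pre-CAE® and post-CAE®, the baseline will be the time point matched value". For an observed score this is Visit 2 (Day 1): post-CAE for staining, ODS and TFBUT, and pre-CAE for Schirmer's.
- **Visit 1.** Protocol 8.3.2 and Appendix 1, and SAP Table 2, schedule all four measures at Day -14 at those same timepoints. SAP 13.1.2, 13.2.1 and 13.2.2 describe ODS, Schirmer's and TFBUT as recorded per eye. For staining, grading of both eyes at Visit 1 is inferred, since the study eye is not yet known at that visit.
- **Other uses of Visit 2.** Protocol 10.4.2 picks the study eye: "the worst eye will be selected as the eye with the worst post-CAE inferior corneal staining at Visit 2", with post-CAE ODS as tie-break. Protocol 4 stratifies randomisation on the same two Visit 2 scores.
- **Entry.** Protocol 4: "two 90-minute exposures to the CAE will be conducted to ascertain eligibility to enter the study", so both Visit 1 and Visit 2 are qualifying visits.

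SAP section 18 (changes from the protocol) adds no Visit 1 covariate.

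**The concern.** Two pre-treatment readings of a noisy measure usually predict a later reading better than one. The trial has a second reading for each of the four endpoints in the testing sequence and does not use it.

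For staining and ODS there is a further reason. The Visit 2 reading also chooses the worse of two eyes and defines strata. A score picked because it was the worse of two tends to carry upward measurement error, which can weaken it as a predictor of Day 29. For Schirmer's and TFBUT the documents show no such role, and the case rests only on having a repeat measurement.

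What is at stake is the width of the confidence intervals. The sample size text in Protocol 10.3 and SAP section 5 counts on adjustment for baseline and site to take power above 90%. Each test after the first is run only if the one before it succeeds, so precision in the early tests carries through the sequence.

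**Working it through.** **1. The plan's own figure.** Inputs from SAP section 5: 60 per arm, two-sided 0.05; staining difference 0.46, SD 0.77; ODS difference 0.49, SD 0.82. Two-sample t-test, noncentral t with 118 df: power is 90.1% for each. The stated figure of about 90% reproduces. At 0.81, the top of the SD range given for staining, the unadjusted test has 87.0%.

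**2. Formula for the gain.** Let r12, r25 and r15 be the correlations between Visits 1 and 2, 2 and 5, and 1 and 5. Adding Visit 1 to a model that already holds Visit 2 multiplies residual variance by 1 − p², where

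p = (r15 − r12·r25) / √[(1 − r12²)(1 − r25²)].

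The documents give none of these correlations. I assume r12 = r25 = r, with r from 0.4 to 0.7, and take r15 either equal to r or 0.1 lower.

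| r | p if r15 = r | variance cut | p if r15 = r − 0.1 | variance cut |
|---|---|---|---|---|
| 0.4 | 0.24/0.84 = 0.286 | 8.2% | 0.14/0.84 = 0.167 | 2.8% |
| 0.5 | 0.25/0.75 = 0.333 | 11.1% | 0.15/0.75 = 0.200 | 4.0% |
| 0.6 | 0.24/0.64 = 0.375 | 14.1% | 0.14/0.64 = 0.219 | 4.8% |
| 0.7 | 0.21/0.51 = 0.412 | 17.0% | 0.11/0.51 = 0.216 | 4.7% |

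Multiplied by 60, the cuts are worth about 5 to 10 subjects per arm in the first case and about 2 to 3 in the second. If r15 = r12·r25 (for example 0.5, 0.5 and 0.25), then p = 0 and nothing is gained.

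**3. Entry selection at both visits.** The real cut-offs are redacted, so this step rests on assumptions throughout. I simulated two eyes (between-eye correlation 0.6; mean 2.3, SD 0.8 on the 0–4 scale), rounded scores to half grades, required an eye to meet a cut-off at both visits, and took the worse eligible eye at Visit 2. With cut-offs of 2.0 or 2.5, the variance cut is about 3% to 12% when r15 = r, and about 1% to 4% when r15 is 0.1 lower. This models staining. ODS is graded in whole steps, and Schirmer's and TFBUT are in mm and seconds, so the simulated figures do not carry over directly to those three.

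**4. Effect on power (staining).** If 0.77 is the SD of raw change, as the text says, and variances are equal across visits, the one-baseline residual SD is 0.77·√[(1 + r)/2].

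- r = 0.4: residual SD 0.644. Power is 97.3% as planned; with Visit 1 it is 98.2% (r15 = r) or 97.6% (r15 lower by 0.1).
- r = 0.7: residual SD 0.710. Power is 94.1% as planned; with Visit 1 it is 97.1% or 95.0%.

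The gain over this range is therefore about 0.9 to 3.1 points, or 0.3 to 0.9 points with the weaker Visit 1 correlation. If 0.77 is read conservatively as already the residual SD, power goes from 90.1% to between 92.3% and 94.5%, or to about 91% with the weaker correlation. These figures ignore site and entry selection.

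**The case against.** The strongest reply is that nothing here is wrong. ANCOVA on each measure's own baseline plus site is valid and prespecified, and on the raw-change reading it already has about 94% to 97% power. That stands, and it limits the point to an optional improvement.

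The reply also weakens several inferences that a reader might draw:

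- **That the models adjust for the Visit 2 score and nothing else.** Site is in every model. Visit 2 is only the sole pre-treatment score.
- **That the Visit 2 score sets the study eye and strata for all four endpoints.** The visible text gives this role to staining and ODS only. Any entry role for Schirmer's or TFBUT is redacted.
- **That Visit 1 is an unselected reading with no part in choosing the study eye.** Eyes are eligible only if they meet the inclusion criteria, and Visit 1 is itself a qualifying visit. An eye-level threshold at Visit 1 could rule an eye out. The criteria are redacted, so this cannot be settled.
- **That 8% to 17% is the expected gain.** That range needs Visit 1 to predict Day 29 as well as Visit 2 does. Visit 1 is nominally 42 days before Day 29 and precedes the 14-day vehicle run-in; Visit 2 is 28 days before and follows it. A weaker correlation for Visit 1 is plausible.

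What survives is that the value is collected before randomisation, so adjusting for it introduces no treatment-related bias. It adds precision whenever it predicts Day 29 beyond what Visit 2 does, and using it needs no new data.

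**Conclusion.** The point holds as a modest missed gain in precision in four models. It is not an error, a bias or a Type I problem, and the documents do not support reading it as a shortfall in power.

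The size depends on correlations that the documents do not give. For assumed values of 0.4 to 0.7, the cut in residual variance runs from 8% to 17% under the favourable assumption, through about 3% to 5% with a slightly weaker Visit 1, to roughly 1% to 4% when entry selection at both visits is added to that, and to nil at the limit. The argument is somewhat stronger for staining and ODS, where the Visit 2 reading also selects the eye and defines strata. For Schirmer's and TFBUT it rests on repeat measurement alone.

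**What to change.** Before unmasking, amend SAP 13.1.1, 13.1.2, 13.2.1 and 13.2.2 as follows.

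- Add the study eye's Visit 1 value of the same measure, at the same CAE timepoint, as a second continuous covariate: `MODEL CHG = BASELINE V1SCORE TREATMENT SITE`. Use the same model in the observed-data, LOCF and PP versions.
- Carry `V1SCORE` in the `VAR` lists of the control-based, missing-at-random MCMC and tipping-point imputations, and also in the predictor lists of the `MONOTONE REG` statements. Those statements name their predictors explicitly, so a change to `VAR` alone would leave Visit 1 out of the regressions.
- Adjust the positional `MINIMUM`, `MAXIMUM` and `ROUND` lists where they are used. In the second imputation step of 13.1.1 they already show four positions against three variables, so each position needs checking.
- State how a missing Visit 1 value is handled.
- Keep Visit 2 as the baseline for change from baseline.

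The cost is one degree of freedom per model and slightly more programming. There is no extra visit, measurement or burden for subjects.

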8.1.4 Procedures for Final Study Entry

Subjects must meet all inclusion and none of the exclusion criteria (Section [5.3](#) and [5.4](#)).

8.1.5 Methods for Assignment to Treatment Groups:

Before the initiation of study run-in at Visit 1, each subject who provides written informed consent will be assigned a screening number. All screening numbers will be assigned in strict numerical sequence at a site and no numbers will be skipped or omitted. Each subject who meets all the inclusion and none of the exclusion criteria at Visit 1 and Visit 2 will be assigned a randomization number at the end of Visit 2. The Interactive Web Response System (IWRS) will be used to assign all randomization numbers.

For the non-Japanese subjects, randomization will be further stratified by the following factors and cut-offs:

Randomization and kit numbers will be assigned automatically to each subject as they are entered into the IWRs.

The site staff will dispense kit(s) required until the next visit. Both the randomization number and the dispensed study drug kit number(s) will be recorded on the subject's source document and electronic case report form (eCRF). Subjects, Sponsor, CRO, and site personnel will be masked to treatment assignment. To ensure masking, a dedicated unmasked staff member/technician will be delegated to dispense and observe instillation of randomized study drug and collect randomized study drug from a subject for drug accountability. This person cannot perform any other study-related procedures.

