10.3 Sample Size

This study is expected to enroll 240 subjects in a 1:1:1:1 ratio across four treatment arms, or 60 subjects per treatment arm. In addition, randomization will be stratified such that [REDACTED] will be randomized in each treatment arm.

The standard deviation (SD) for change from baseline in post-CAE inferior corneal fluorescein staining ranges between 0.68 and 0.81 units. Assuming a common SD of 0.77, a sample size of 60 subjects per group will have approximately 90% power to detect a difference of 0.46 units between the active treatment group and the vehicle group using a two-sample t-test at a two-sided significance level of 0.05. Again, it is assumed that adjusting for baseline and site will further reduce variability and provide >90% power.

Likewise, the SD for change from baseline scores in the post-CAE ODS at Day 29 is assumed a common SD of 0.82, a sample size of 60 subjects per group will have approximately 90% power to detect a difference of 0.49 units between the active treatment group and the vehicle group using a two-sample t-test at a two-sided significance level of 0.05. It is assumed that adjusting for baseline and site will further reduce variability and provide >90% power.

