10.4.5 Efficacy Analyses

Primary Efficacy Analyses

The primary comparisons of change from baseline in post-CAE inferior corneal staining and ocular discomfort between the [REDACTED] K-161 [REDACTED] group and the vehicle group at Day 29, will be performed using analysis of covariance (ANCOVA) models. The respective baseline post-CAE score will be included as a covariate in each model and site will be included as a fixed effect. Treatment by baseline and treatment by site interactions will be explored in separate models and, if significant, analyses will be performed by baseline stratification and/or site, respectively, to further examine significant interactions. The primary analyses will use the ITT population.

For the primary endpoints, multiple imputation with MCMC techniques will be used. Imputation will be performed by treatment arm with imputation terms for baseline and Day 29 scores.

Secondary Efficacy Analyses

Secondary and exploratory endpoints will be analyzed similarly to the primary analyses on the ITT population. Continuous and ordinal variables collected at each visit will be summarized descriptively (n, mean, standard deviation, median, minimum and maximum), and analyzed with ANCOVA models comparing each K-161 group to the vehicle group. All visit-based data will be analyzed by visit and for each timepoint, if applicable, as well as the change from baseline.

Data collected pre- and post-CAE will also be analyzed for the change from pre- to post-CAE within each visit. Data collected during the CAE will also be analyzed using repeated measures models including all of the time points from a CAE exposure.

For the two important secondary endpoints, other secondary, and exploratory endpoints, multiple imputation with MCMC techniques will be used. Imputation will be performed by treatment arm with imputation terms for baseline and Day 29 scores.

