The standard deviation (SD) for change from baseline in post-CAE® inferior corneal fluorescein staining ranges between 0.68 and 0.81 units. Assuming a common SD of 0.77, a sample size of 60 subjects per group will have approximately 90% power to detect a difference of 0.46 units between the active treatment group and the vehicle group using a two-sample t-test at a two-sided significance level of 0.05. Again, it is assumed that adjusting for baseline and site will further reduce variability and provide >90% power.

Likewise, the SD for change from baseline scores in the post-CAE® ODS at Day 29 is assumed a common SD of 0.82, a sample size of 60 subjects per group will have approximately 90% power to detect a difference of 0.49 units between the active treatment group and the vehicle group using a two-sample t-test at a two-sided significance level of 0.05. It is assumed that adjusting for baseline and site will further reduce variability and provide >90% power.

6. Data Preparation

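### Each of the four hierarchical ANCOVAs leaves out at least one named randomization factor; if that factor is prognostic, the reported standard error is too large and the test mildly conservative

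*SAP*

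**What the plan says.** **Randomization.** Protocol section 4 states: "Randomization will be stratified on Visit 2 Post-CAE inferior fluorescein staining and", and the sentence continues "Post-CAE ocular discomfort on the Ora Calibra® scale". Protocol 8.1.5 and SAP 4.1 limit the score strata to part of the sample: "For the non-Japanese subjects, randomization will be further stratified by the following factors and cut-offs". The list of factors and cut-offs that should follow is redacted.

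**Analysis.** For the two primary endpoints, Protocol 10.4.5 says: "The respective baseline post-CAE score will be included as a covariate in each model and site will be included as a fixed effect". The SAP follows this:

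| Step | Endpoint (SAP section) | Baseline term in the ANCOVA | Named stratification score left out |
|---|---|---|---|
| 1 | Inferior staining (13.1.1) | staining | ODS |
| 2 | ODS (13.1.2) | ODS | staining |
| 3 | Schirmer's test (13.2.1) | Schirmer's | staining and ODS |
| 4 | TFBUT (13.2.2) | TFBUT | staining and ODS |

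All four also contain site and treatment. For step 1 the code is "MODEL CHG = BASELINE TREATMENT SITE/ SOLUTION COVB", with the baseline term defined as inferior staining alone.

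**Sensitivity analyses.** The ANCOVA for observed data, LOCF and the PP population repeats the same model. The two-sample t-tests and Wilcoxon tests carry no covariates. The by-stratum analyses split on an endpoint's own baseline or on site and do not bring in the other score. SAP section 18 does not mention the matter.

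**The concern.** A trial that stratifies its allocation on a score has judged that score worth balancing. Stratification makes the arms more alike on it, so the treatment estimate varies less from one randomization to the next. An ANCOVA without the score does not know this. Any outcome variance the score explains stays in the residual, and the reported standard error describes a less well-balanced trial than the one run.

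At stake are confidence intervals that are somewhat too wide and a test that rejects slightly less often than its nominal level. Testing is in fixed sequence, so a conservative first test also holds back the steps behind it. The remedy uses data already collected, so the question is how much it would return.

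**Working it through.** **1. The plan's own power.** SAP section 5 says that "a sample size of 60 subjects per group will have approximately 90% power to detect a difference of 0.46 units" at SD 0.77 (two-sample t-test, two-sided 0.05).

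- Staining: SE = 0.77 × √(2/60) = 0.1406; 0.46/0.1406 = 3.272; noncentral t on 118 df gives 90.1%.
- ODS: SE = 0.82 × √(2/60) = 0.1497; 0.49/0.1497 = 3.273; power 90.1%.

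The stated figure reproduces. The standardized effects are 0.597 and 0.598, so the staining results below serve for ODS too.

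**2. Why a simple formula is not enough.** Multiplying the SE by √(1 − R²) gives √0.90 = 0.949 at R² = 0.10. That credits the whole reduction to the added covariate, although stratified allocation has already delivered part of it. The model SE and the true spread of the estimate must be tracked separately, which needs simulation.

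**3. Simulation.** From the documents: 240 subjects, four equal arms, difference 0.46, SD 0.77, score strata within non-Japanese subjects only. Assumed, because the documents do not give them: 25% Japanese (one stratum), 8 sites, blocks of 4, correlation 0.3 between the two scores, and about half of subjects above each cut. The cut at 3.0 is borrowed from the subgroup rule in SAP 13.1.1 ("Analyses will be performed by baseline stratification (≤ 3.0 and >3.0) and/or site"). R² is the share of variance the omitted score explains after own baseline and site. Each scenario has 20,000 complete-data trials, with 0.77 provisionally used as the SD after adjustment. Staining endpoint, without → with ODS:

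| R² | Model SE | True SD of estimate | Type I error | Power |
|---|---|---|---|---|
| 0 | 0.1426 → 0.1428 (+0.1%) | 0.1419 → 0.1421 (+0.1%) | 4.9% → 5.0% | 89.7% → 89.6% |
| 0.05 | 0.1429 → 0.1392 (−2.6%) | 0.1411 → 0.1393 (−1.3%) | 4.8% → 5.0% | 89.6% → 90.8% |
| 0.10 | 0.1431 → 0.1355 (−5.3%) | 0.1390 → 0.1356 (−2.4%) | 4.3% → 5.0% | 89.9% → 92.2% |

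About half of the fall in the model SE is a real gain in precision. The rest brings the reported SE down to the spread the estimate already had.

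**4. Correcting the SD basis.** SAP section 5 gives 0.77 for an unadjusted t-test and expects adjustment for baseline and site to reduce it. If those terms explain a share v of the variance, both columns above shrink by k = √(1 − v), and

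power ≈ Φ[(0.46 − t × k × SE_model) / (k × SD_true)], with t = 1.970.

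Example, R² = 0.10 and v = 0.10 (k = 0.9487):

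- Without ODS: (0.46 − 1.970 × 0.1358)/0.1319 = 1.46, or 92.8%.
- With ODS: (0.46 − 1.970 × 0.1285)/0.1286 = 1.61, or 94.6%.

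| v (assumed) | R² = 0.05 | Gain | R² = 0.10 | Gain |
|---|---|---|---|---|
| 0 | 89.7% → 90.9% | 1.2 | 90.0% → 92.3% | 2.3 |
| 0.10 | 92.5% → 93.5% | 1.0 | 92.8% → 94.6% | 1.8 |
| 0.20 | 95.0% → 95.8% | 0.7 | 95.3% → 96.6% | 1.3 |
| 0.30 | 97.1% → 97.6% | 0.5 | 97.3% → 98.1% | 0.8 |

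Gains are in percentage points, taken before rounding. The percentage changes in SE do not depend on v.

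**5. Schirmer's and TFBUT, both scores missing.** On an arbitrary scale:

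- R² = 0.10: model SE 0.1433 → 0.1359 (−5.2%), true SD 0.1389 → 0.1358 (−2.2%).
- R² = 0.20: model SE 0.1436 → 0.1281 (−10.8%), true SD 0.1343 → 0.1278 (just under −5%).

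The documents give no effect or SD for these endpoints, so no power figure follows.

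**6. Robustness.** At R² = 0.10, varying the Japanese share (10% or 50%), block size (8) and score correlation (0 or 0.5) left the model SE 5.2–5.3% smaller and the power gain, at v = 0, at 2.1–2.4 points. A separate simulation with strata over all subjects and a partial correlation of 0.3 (R² = 0.09) gave model SE 0.1427 → 0.1361, type I error 4.5% → 5.1%, and power 89.4% → 91.7%.

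**The case against.** The case against is strong on size. Protocol and SAP specify the same model, and the power statement names the same adjustment. Each primary model already carries one of the two scores as a continuous covariate. Nothing in the documents shows that baseline discomfort predicts change in staining, or the reverse, so every non-zero figure rests on an assumed R². Treating 0.77 as an adjusted SD flatters the gain. The calculations also use complete data, whereas the planned primary analysis is control-based multiple imputation followed by ANCOVA.

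All of that stands, and the range in step 4 reflects the SD point. It does not remove the omission, which is legible in all four models. Redaction limits only one statement: SAP section 17, most of section 14 and much of Protocol 10.4.7–10.4.10 are blacked out, so one can say only that no visible analysis adds the missing score.

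A reader might infer more than the documents support:

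- *Inflated type I error or a biased estimate.* Neither follows. The treatment effect is protected by randomization, and without the score the simulated type I error was at or below 5%.
- *An underpowered trial.* The planned power of approximately 90% is met without the extra terms.
- *A SAP that departs from its protocol.* It does not; the omission is in both.
- *Japanese status as a further missing factor.* The wording about non-Japanese subjects, and the Protocol 10.3 sentence beginning "In addition, randomization will be stratified such that", suggest such a stratum, but the operative text is redacted. It remains an inference.

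**Conclusion.** The point holds as an optional, low-cost improvement in efficiency and calibration. If the omitted score is prognostic, the plan reports a standard error that is too large: adding the score makes it about 2.6% smaller at R² 0.05 and 5.3% smaller at R² 0.10. The likely power gain per primary test is about 0.5–1.0 or 0.8–1.8 points, provided own baseline and site explain 10–30% of variance. The 1.2 and 2.3 point figures are upper ends for those two R² values. If the score is not prognostic, nothing material is lost either way.

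These sizes rest on assumed prognostic strength, sites, block size, cut-offs and Japanese share, and on complete data. The omission itself rests on legible text and needs none of those assumptions.

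**What to change.** Before unmasking:

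- Add the study-eye Visit 2 post-CAE ODS to the staining ANCOVA, the study-eye Visit 2 post-CAE inferior staining to the ODS ANCOVA, and both to the Schirmer's and TFBUT ANCOVAs, as continuous covariates.
- Use the same terms in the observed-data, LOCF, MCMC, PP and tipping-point ANCOVAs, so that each sensitivity analysis tests the same model as the primary.
- Put the terms in the PROC MI models too. Otherwise missing outcomes are imputed without a score the analysis then conditions on, which pulls that score's coefficient toward zero. Respecify the VAR and MONOTONE REG lines and, where they are kept, the positional bounds and rounding lists. In SAP 13.1.1 the second-step lists already hold four values for three variables, so they need checking anyway.
- Give the added ODS covariate a name other than ODS_BASE, which SAP 13.3.8.2 already uses for the timepoint-matched baseline during CAE.
- Add Japanese status only if the unredacted scheme confirms it as a stratification factor, after checking its overlap with site.
- Record the change in SAP section 18.

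**Cost.** One residual degree of freedom for staining and ODS, two for Schirmer's and TFBUT, out of about 228 (240 − 4 arms − 1 baseline − 7 for an assumed 8 pooled sites). If the scores are not prognostic, the SE rises by about 0.1–0.2%. Four endpoints and their sensitivity and imputation code need reprogramming. No new data are required: both scores are scheduled post-CAE at Visit 2 (Protocol Appendix 1, SAP Table 2).
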